4.3.2. Secondary Endpoints

Several secondary endpoints will be collected to evaluate what effect, if any, the interventions have on each measure.

Analyses may also explore the effect of the actual intervention(s) received on these secondary endpoints. Secondary efficacy endpoints for the following outcome measures will be assessed at 3 months after start of treatment, unless otherwise stated:

- Proportion success evidenced by $\geq 30\%$ reduction in pain interference as measured using Question #9 of the BPI-SF (BPI-9) compared to baseline
- Proportion with clinically significant change (≥ 10 -point reduction) in disability as measured using the Oswestry Disability Index (ODI) compared to baseline
- Durability of primary endpoint, proportion success with $\geq 50\%$ reduction in average back pain intensity, at 6- to 24-months after start of treatment
- Proportion success with $\geq 50\%$ reduction in worst back pain intensity as measured using Question #3 of the BPI-SF (BPI-3) compared to baseline
- Average Patient Global Impression of Change (PGIC)

- Average change in health-related quality of life as measured using the EQ-5D compared to baseline
- Average change in analgesic medication usage (e.g., opioids, non-opioids, and total analgesic medication usage)

Brief Pain Inventory-Short Form (BPI)

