5.3. Visit 3 – Medial Branch Block or Diagnostic Procedures

A diagnostic medial branch block (MBB) or other diagnostic procedure (e.g., SCS trial, imaging, etc.), as deemed appropriate by the physician for subjects in Group 2, will be completed at or following Visit 3. Visits 2 and 3 may occur on the same day.

The following measures will be assessed at this visit for both groups:

- Selected questions from Brief Pain Inventory (BPI) (e.g., BPI-3, BPI-5)
- Current pain treatments/analgesic usage

GROUP 1 – Medial Branch Block

Subjects will undergo a standard diagnostic medial branch block (MBB) targeting the area where they have chronic low back pain. Provocative maneuvers or positions which normally exacerbate their typical pain may also be assessed and documented before and after the procedure to help determine effect of MBB.

The diagnostic medial branch block (MBB) will be performed according to standard practice using aseptic technique. [REDACTED]

[REDACTED]

[REDACTED]

[REDACTED]

[REDACTED]

Pain scores will be collected post-procedure to evaluate the impact of the MBB. Subjects in Group 1 (PNS) will proceed to Visit 4 (PNS Lead Placement) after a single MBB (Visit 3), regardless of the outcome.

If a subject has previously undergone a diagnostic lumbar medial branch block (MBB) within 3 months of the baseline visit, and results and medical records are available from that block, a subject is not required to complete an additional block at this visit. However, procedure details and results from the procedure should be documented in the CRFs. If a subject previously underwent the MBB and results are not available, the subject should complete the visit, repeating the MBB as part of the study.

GROUP 2 - Diagnostic Procedures

Subjects in Group 2 will receive standard of care diagnostic testing and/or interventions (e.g., Medial Branch Block, SCS trial, MRI, etc.) for their low back pain as they usually would if not participating in the study. All diagnostic tests or interventions received by Group 2 subjects will not be paid for through the study. Subjects should follow their insurance requirements (e.g., prior authorization) for these procedures. [REDACTED]

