8.1. Plan to maximize subject retention and minimize loss of data

Significant efforts will be made to maintain maximum subject retention and follow up data and minimize the percentage of missing data.

Prior experience indicates a potential cause of data loss is when a lead is dislodged or removed before scheduled end of PNS therapy (60 days).

Additional instructions have been provided regarding bandaging to the subjects to minimize the chance of accidental lead dislodgement.

Subject withdrawal from the study is a potential source of data loss. Study investigators and staff will be trained to have clear discussions with subjects considering withdrawing from the study. During the discussions, subjects will be reminded that they may withdraw from the study at any time and investigators will determine if any burdens of continuing in the study can be eased to enable participation at a level that is more amenable to the subject. For example, if subjects indicate a lack of interest in continued participation, they can be offered an opportunity to provide only the most essential and easily collectable data (e.g., recall pain scores and AE questions regarding their safety). To further reduce burden associated with time and travel to the clinical site, subjects can be provided with the option to complete AE questions, surveys, or diaries over the phone or return these via other methods (e.g., a preaddressed, postage-paid envelope, email, ePro, etc).

Subjects in either group may continue to participate in the study visits independent of their successful completion of diagnostic procedures and/or standard interventional management. These subjects may be offered the option to continue with the study and provide only the most essential and easily collectable data (including the option of switching to all telephone calls and completing the most important visits). Subjects also have the option to receive SOC LBP treatments from their regular, outside medical providers (i.e., not exclusively from the study site). If so, these subjects will continue to be followed by the site for research only visits/calls. Alternative options may be utilized to minimize data loss in subjects.

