Subjects may elect not to undergo a diagnostic procedure and/or treatment (e.g., subject elects to continue their usual care for back pain) but are still willing to remain in the study. In this event, if the subject has not undergone a diagnostic procedure by the end of the Visit 3 window, they will progress directly to Visit 4 (i.e., Visit 3 will be marked as "missed" and Visit 4 will be completed via phone). Regardless of the mode of participation, subjects

who continue participation through 12 months after "Start of Treatment" (completion of Visit 16) will be eligible for crossover.

Subjects are offered compensation for each visit as it is completed, including unscheduled visits, even if they do not complete all the visits. This compensation is intended to cover costs associated with taking the time to participate in the study. [REDACTED]

A potential source of data loss is the failure of the subjects to return their completed diaries. Thus, subjects may receive reminder calls from the clinical study staff before certain visits to remind them to bring their completed diaries with them to the visit. For long-term follow up visits, subjects may complete a diary after a visit and return via mail/email if the original diary for that visit was lost or was not completed. Diaries may also be completed electronically.

If a subject is unable to return any follow-up diary, the data may be replaced using the one-week recall data (question #3 or #5 of the validated BPI-SF). If the subject later returns the diary, the diary data will be used over the one-week recall data. If a subject is unable to return to the clinic for a visit, options to collect the most important assessments (e.g., pain intensity, ODI) and data (e.g., LBP treatment use, adverse events, etc.) will be made available to the subject (e.g., assessment of surveys and visit questions via phone or video call, remote completion of surveys via mail, email, ePro, etc.). These options will mitigate the problem of missing data and minimize the need to impute scores. Scores will only be imputed if recall (or remotely collected) data are unavailable and cannot be obtained.

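### Section 8.1 lets subjects whose procedure was not completed give reduced data, and no example set names BPI-9, PGIC or EQ-5D, so 3-month secondary data may be missing unevenly between groups

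*Protocol*

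**What the plan says.** Section 4.3.2 sets the timing: "Secondary efficacy endpoints for the following outcome measures will be assessed at 3 months after start of treatment, unless otherwise stated". Six measures fall at that time: BPI-9, ODI, BPI-3, PGIC, EQ-5D and analgesic use. Durability of the primary endpoint is assessed later, from 6 months on. Section 8.0 says that all primary and secondary outcome data will be analysed and reported.

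Section 8.1 then describes lighter follow-up in three situations.

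- **Subjects thinking of withdrawing.** They can be offered the chance to give "only the most essential and easily collectable data (e.g., recall pain scores and AE questions regarding their safety").
- **Subjects whose procedure was not completed.** The passage opens "Subjects in either group may continue to participate in the study visits independent of their successful completion of diagnostic procedures" and/or standard interventional management. It continues "These subjects may be offered the option to continue with the study and provide only the most essential and easily collectable data", and explains this as "including the option of switching to all telephone calls and completing the most important visits".
- **Subjects who cannot attend.** Here, and in sections 5.5, 5.6 and 5.7, the protocol promises "options to collect the most important assessments (e.g., pain intensity, ODI"), together with back-pain treatment use and adverse events.

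Sections 5.5 to 5.7 and 8.1 also allow questionnaires to be completed remotely, by phone, mail, email or ePRO.

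**The concern.** The second situation differs from the other two. A subject who is about to withdraw, or who cannot travel, presents a practical obstacle, and some data are better than none. A subject whose procedure was not completed need not be reluctant at all. Sections 5.4 and 8.1 expressly describe people who decline a procedure yet are content to stay in follow-up. For them the alternative to the reduced set is fuller follow-up, not loss of the subject.

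The offer therefore ties the amount of data collected to an event after randomization that is related to treatment received and is likely to be unequal between groups. If BPI-9, PGIC and EQ-5D are not asked at Visit 13, the 3-month comparison of those measures is between differently selected parts of the two groups. Analysis cannot restore what was never asked. It can only substitute assumptions about subjects who may differ systematically from those observed.

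**Working it through.** The protocol states no figure on this point, so there is none to reproduce. The check has three parts.

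**1. Coverage of the six 3-month secondary measures by the example sets**

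| Measure | Recall pain and AEs (8.1, subjects losing interest) | Pain intensity, ODI, treatment use, AEs (5.5–5.7 and 8.1, subjects unable to attend) |
|---|---|---|
| BPI-3 | covered by recall | covered |
| ODI | not named | named |
| Analgesic use | not named | only if treatment use is read to include it |
| BPI-9 | not named | not named |
| PGIC | not named | not named |
| EQ-5D | not named | not named |

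The first set leaves 5 of 6 unnamed. The second leaves 4 of 6, or 3 of 6 if treatment use covers analgesics. If the subject completes all surveys and diaries remotely, none need be lost. BPI-5, the primary measure, is kept under both sets.

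**2. Who meets the trigger**

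- Section 5.3: Group 1 subjects "will proceed to Visit 4 (PNS Lead Placement) after a single MBB (Visit 3), regardless of the outcome". A negative block therefore does not stop a Group 1 subject from being treated.
- Section 5.3: a Group 2 subject can fail the block and so not receive RFA, and must meet insurance requirements for procedures that the study does not pay for.
- Section 5.4: a Group 2 subject may choose no procedure and stay in the study.
- Standard interventional management, the second half of the trigger, is the Group 2 treatment.

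The wording covers either group, but the routes to non-completion lie mainly in Group 2.

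**3. Size, on assumptions**

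Let m be the fraction of Group 2 with the measure missing, a the success rate in those observed and b the rate in those missing. Group 1 is taken as complete.

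- Observed-case rate = a
- Full-group rate = (1 − m)a + mb
- Overstatement = a − [(1 − m)a + mb] = m(a − b)

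Section 4.2.6 gives at most 230 subjects at 1:1, so 230/2 = 115 per group. The rates a = 0.50 and b = 0.20 are assumed.

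| m | Group 2 observed, 115(1 − m) | Full-group rate | Overstatement |
|---|---|---|---|
| 10% | 103.5 | 0.90 × 0.50 + 0.10 × 0.20 = 0.47 | 3 points |
| 20% | 92 | 0.80 × 0.50 + 0.20 × 0.20 = 0.44 | 6 points |
| 30% | 80.5 | 0.70 × 0.50 + 0.30 × 0.20 = 0.41 | 9 points |

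Only the gap a − b matters, not the level. With a 10-point gap the same fractions give 0.10 × 10 = 1 to 0.30 × 10 = 3 points, and with no gap there is no bias. For PGIC and EQ-5D, which are averages, the same formula holds with means in place of rates.

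Loss of precision is the smaller issue. For assumed rates of 0.70 against 0.50 at two-sided 0.05, power with 115 per group is 87.7%. It falls to 85.9%, 83.8% and 81.0% when 10%, 20% and 30% of Group 2 are missing.

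**The case against.** The other side has several good points, and they limit what can be claimed.

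- **Loss by design.** A reader might infer that most secondary endpoints are lost by design. The text does not support that. The offers are discretionary, the lists are examples rather than closed sets, remote questionnaires are allowed, and section 5.7 keeps the Appendix B schedule as the default. Appendix B is not legible in the public copy, so what it requires by phone cannot be checked.
- **One list for everyone.** A reader might apply the pain-and-AE list to subjects whose procedure was not completed. That list is attached only to subjects losing interest. The passage on non-completion describes phone contact and the most important visits, and Visit 13, which carries the primary endpoint, is plausibly one of those. A site could carry the example over, because the same phrase is repeated shortly afterwards, but that is inference.
- **Untreated controls.** Non-completion is not the same as no treatment. Sections 5.3, 5.4 and 8.1 allow other treatments, later procedures and outside care.
- **Conflict over ODI.** The two example lists differ on ODI, but they serve different situations, so this is not a contradiction.
- **Analysis.** Handling of missing data may properly be left to the SAP.
- **Burden.** A fuller set at Visit 13 asks more of subjects, and protecting the primary data first is a legitimate choice.

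All of this stands. It does not remove the central point. No section fixes a minimum 3-month data set, three secondary measures appear in no example, and willing subjects may be moved to reduced collection because of what happened to their procedure.

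**Conclusion.** The concern holds as a weakness in what the protocol permits, and it is worth correcting. Section 8.1 allows 3-month data on BPI-9, PGIC and EQ-5D to go uncollected for a reason that is linked to treatment received and falls mainly on Group 2. Concentration in Group 2 is an inference from sections 5.3 and 5.4, because the text itself says either group.

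The size is unknown. The 3 to 9 points are an illustration, not an estimate. They assume that 10% to 30% of Group 2 lack the measure, that those subjects' success rate is 30 points lower, that Group 1 is complete, and that observed cases are analysed without adjustment. On those assumptions the error flatters the control group and works against PNS. If the missing subjects did better than the rest, the direction would reverse. The primary endpoint is not affected through this route, because BPI-5 is kept, and BPI-3 is kept as well.

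**What to change.** In sections 5.7 and 8.1, state that non-completion of a diagnostic procedure or of standard interventional management does not reduce the Visit 13 data set. In both groups, every subject still willing to take part is asked BPI-5, BPI-3, BPI-9, ODI, PGIC, EQ-5D and current analgesics, by the existing phone, mail or ePRO channels if not in clinic. Pain items come first, so that the primary data are secured if the subject stops early.

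Keep the pain-and-AE-only set for other visits. At Visit 13, reserve it for subjects who would otherwise withdraw.

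The cost is a few more minutes at one contact for subjects on lighter follow-up, with no new collection channel. The downside is a small risk of partial completion. Asking pain first limits that risk, although it does not help with a subject who declines the contact altogether.

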8.2. Safety Endpoint Analysis

All study-related adverse events will be documented, reported, and categorized.

9.0 STUDY TRAINING, MONITORING, AND DEVICE ACCOUNTABILITY PROCEDURES

9.1. Study Training

SPR Therapeutics or their designee will conduct a Site Initiation and Training Visit prior to initiation of the study. The purpose of this visit will be to develop a common

understanding of the clinical protocol, Case Report Forms (CRFs), study specific procedures, Investigator Responsibilities, and Good Clinical Practices (GCPs) among SPR and the Clinical Site team.

9.2. Study Monitoring

9.2.1

SPR Therapeutics or a designated qualified study monitor will monitor this study. Other appropriately qualified clinical monitors may also be involved in the monitoring of study sites. Monitoring visits to the Clinical Site will be conducted periodically, as determined by the rate of subject enrollment, during the study to ensure that the most currently approved version of the Investigational Plan is being followed and that the site is in adherence with all Good Clinical Practices and any specific study Data Monitoring Plan that is in place. In addition, source documents will be reviewed for accuracy against data found on the Case Report Forms.

The Clinical Site will maintain all source documentation in either paper or electronic format. SPR Therapeutics clinical monitors or their authorized representatives will be granted access to these source documents during each visit for verification against the CRFs. The site regulatory files will be reviewed during monitoring visits, as needed, to ensure that current amendments and approvals have been obtained.

The study records may also be subject to a quality assurance audit by SPR Therapeutics (or their authorized representatives), as well as inspection by appropriate regulatory authorities. Site personnel are required to be available during the monitoring visits and audits and ensure that sufficient time is dedicated to this process.

9.2.2

9.3. Device Accountability

Devices will be used from the site's commercially available stock. Site will report all device usage to SPR for device accountability and device tracking purposes.

9.3.1 Returning used devices to SPR Therapeutics

If a device needs to be returned to SPR, the site will contact SPR for instructions prior to returning any devices.

9.4. Independent Clinical Events Reviewer

An independent Clinical Events Reviewer will be utilized for this study to adjudicate all adverse events (AEs). AE information, including group assignment, will be provided to the Reviewer. In these situations, the adjudication by the Clinical Events Reviewer will be the final determination.

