4.3.1.2. Primary Safety Endpoint

The primary safety endpoint is the occurrence and type of study-related adverse events. For Group 1 (PNS), all adverse device effects (ADEs) that occur during the study will be documented. For group 2 (standard interventional management), all study-related adverse events will be documented. For both groups, AEs related to standard of care (SOC) will be collected. Specific details regarding any study-related AE will be collected on an Adverse Event Form and will be followed to resolution. The investigator will determine the severity of each event as well as its relationship to the study (i.e., device and procedure). In addition, each event will be categorized as either serious or non-serious. Any necessary treatment or intervention required and the resolution status of the event will also be documented. Study-related AEs will be tabulated and summarized at the conclusion of study. Additional details on the monitoring and adjudication of study-related AEs is described in the section regarding monitoring.

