8.0 DATA ANALYSIS AND STATISTICAL METHODS

All primary and secondary outcome data will be analyzed and reported. Each clinical site or individual clinician may be analyzed separately. The study objective is to compare the safety and effectiveness of percutaneous PNS for the treatment of low back pain to standard interventional management. The study will determine if the treatment effect of percutaneous PNS is equivalent (i.e., statistically non-inferior), and if so, if it is superior, to standard treatment with standard interventional management.

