9.6. Adverse Events

An Adverse Event (AE) is defined as any untoward medical occurrence in a patient whether or not related to the medical device or procedure. Adverse Events will not be captured unless they are study related or the relationship is unable to be determined.

An Adverse Device Effect (ADE) is a study-related Adverse Event. Adverse Device Effects (ADEs) that occur during the study, include AEs related to SOC, will be captured on an Adverse Event Form and reported to the Sponsor. If the relationship of the adverse event to the System is not able to be determined, it will be captured on an Adverse Event Form and reported to the Sponsor. Specific details regarding the ADE, including the event category, severity of event, and seriousness will be collected. Any necessary treatment or intervention required and the resolution status of the ADE will also be documented. ADEs will be followed to resolution. Any ADEs related to the SPRINT PNS System that meet the requirements for Medical Device Reporting (MDR) will be entered into SPR's complaint system. For SOC-related events, the sites will follow their internal policies for Medical Device Reporting (MDR).

All ADE's are further categorized as anticipated or unanticipated. Any ADE's specified in the Risk Analysis of this protocol will be considered "anticipated". All other ADE's are considered "unanticipated". Anticipated events that occur with a greater frequency than expected are also considered unanticipated.

An Unanticipated Adverse Device Effect (UADE) is defined as any serious adverse effect on health or safety or any life threatening problem or death caused by, or associated with, a device, if that effect, problem or death was not previously identified in nature, severity or degree of incidence in this protocol or application or any other unanticipated serious problem associated with a device that relates to the rights, safety or welfare of subjects.

Study Personnel will report any UADE by telephone and email to SPR Therapeutics within 24 hours of learning of the event. The event is reported by telephone and a completed AE form will be emailed to SPR Therapeutics staff as indicated in **Table 2**. Follow-up information and the complete UADE report will be forwarded to SPR Therapeutics as the event continues and/or resolves.

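### Section 9.4 discloses group assignment to the Clinical Events Reviewer for every adverse event, leaving severity, seriousness and shared event categories needlessly open to bias by arm

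*Protocol*

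**What the plan says.** Protocol Section 9.4 sets up the review: "An independent Clinical Events Reviewer will be utilized for this study to adjudicate all adverse events (AEs". It then fixes what the Reviewer sees, "AE information, including group assignment, will be provided to the Reviewer", and the standing of the outcome: "the adjudication by the Clinical Events Reviewer will be the final determination".

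Section 4.3.1.2 describes the first rating, made at the site: "The investigator will determine the severity of each event as well as its relationship to the study (i.e., device and procedure". It continues: "In addition, each event will be categorized as either serious or non-serious". It refers to the monitoring section for adjudication details. The same section defines what is counted: "The primary safety endpoint is the occurrence and type of study-related adverse events".

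Section 8.0 makes safety a comparison between the arms: "The study objective is to compare the safety and effectiveness of percutaneous PNS for the treatment of low back pain to standard interventional management". Section 4.1 states the same purpose. Section 9.6 limits what enters the database: "Adverse Events will not be captured unless they are study related or the relationship is unable to be determined".

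The text shown describes no masking of subjects, investigators or the Reviewer.

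**The concern.** The two treatments cannot be mistaken for each other. Group 1 has percutaneous leads and an external stimulator for eight weeks. Group 2 receives ablation, spinal cord stimulation, surgery or other standard care. The protocol does not call itself open-label, but nothing in it hides the arm from the site. The first rating of every event is therefore made by someone who knows the treatment and in most cases delivered or directed it.

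A central reviewer offers a chance to judge at least part of each event without that knowledge. Section 9.4 gives this up for every attribute of every event. It does so by an express instruction, so this is not a detail left to another document. Who sees group assignment is a matter of trial conduct, and an analysis plan could not repair it afterwards. There is one Reviewer, not a panel, and the ruling is final, so a tendency to rate like events differently in the two arms would meet no described counterweight.

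At stake is the credibility of the between-arm description of severity, seriousness and, for some events, type. Seriousness also enters the definition of an unanticipated adverse device effect in Section 9.6.

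**Working it through.** No arithmetic applies. The protocol states no figure on this point, gives no adverse event rates and, in the text shown, specifies no between-arm safety test: Section 4.3.1.2 speaks of tabulating and summarising, and Section 8.2 of documenting, reporting and categorising. The check is to take each attribute of an event in turn and ask whether judging it requires the group, and what depends on it.

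1. **Relationship to device or procedure** (Sections 4.3.1.2 and 9.6). The group is required, because an event cannot be attributed to a treatment without knowing which treatment was given. This attribute decides whether an event counts in the primary safety endpoint.
2. **Anticipated or unanticipated status** (Section 9.6). The group is required. Status is judged against the protocol's own risk analysis, and the risks listed in Section 10.2 mainly concern PNS (introducer needle, lead exit site, lead breakage, pads and bandages).
3. **Severity** (Sections 4.3.1.2 and 9.6). The group is not required. Severity can be rated from what happened to the subject. It describes events and does not decide whether they are counted.
4. **Seriousness** (Sections 4.3.1.2 and 9.6). The group is not required, for the same reason. It also describes events, but feeds the definition of an unanticipated adverse device effect.
5. **Event category, or type.** This is mixed. A lead exit-site event names its arm. Increased pain, or an event after a medial branch block, need not. Section 5.3 has Group 1 undergo a block unless a documented one exists from within 3 months of baseline, and allows Group 2 to have one. Section 10.2 names block risks and discomfort or increased pain, although most of its detail is blacked out and it lists only study-specific risks. That these events can arise in both arms is thus inferred from the procedures; the protocol does not state it. Type is part of the primary safety endpoint, so this is the one place where masking would reach that endpoint.

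Attributes 3 and 4, and the shared part of attribute 5, are therefore unmasked without need. Attributes 1 and 2 are unmasked of necessity.

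The remit also needs checking. Section 9.4 does not say which attributes the Reviewer rates. That severity and seriousness are included is inferred from the instruction to adjudicate all adverse events, read with Section 4.3.1.2. If they are not included, the investigator's rating stands, and it too is made with knowledge of the arm. The exposure exists on either reading.

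**The case against.** The strongest reply is that the fix misses the main route for bias. The endpoint is occurrence and type of study-related events. Rating an event milder or non-serious leaves it in the count. Relatedness decides what is counted, and there the group must be known. Site capture comes earlier still, since only related or undeterminable events are recorded. All of this stands, and it limits the weight of the point.

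A second reply is that redaction will often fail because device-specific narratives identify the arm. This also stands. Partial masking still protects the shared events, whereas the present text protects none.

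A reader might go further in three ways that the protocol does not support:

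- *The review gives no protection at all.* The protocol calls the Reviewer independent and never says that the role exists to mask by arm. A reader outside the sites can still guard against inconsistency between sites and against investigator interest.
- *The Reviewer's ruling replaces the site's rating.* The sentence on finality refers back to situations that the text shown does not specify. Nothing says that investigator ratings, which are recorded on the Adverse Event Form, are discarded.
- *The chance of a false safety difference can be quantified.* That would require event rates, a rate of one-sided re-rating and a between-arm test. The protocol gives none of these, so any such figure would describe an analysis that it does not state.

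**Conclusion.** The point holds in a limited form. Section 9.4 expressly unmasks the only rater who could have been masked, for attributes that do not need it, in a trial that sets out to compare safety between visibly different arms. The attributes affected are severity, seriousness and the category of events that both arms can have.

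The size is qualitative. The first two are supporting descriptors; the third touches the type component of the primary safety endpoint for an unknown share of events. The conclusion assumes that the Reviewer's remit includes these attributes, which is inferred, and that a useful share of narratives can be redacted without revealing the arm, which the protocol gives no means to judge. It does not show that the safety results will be biased, and it does not bear on the primary efficacy comparison. The change should be made because it is cheap and improves on a stated rule; the trial's main conclusion does not depend on it.

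**What to change.** Amend Section 9.4 as follows.

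1. List the attributes that the Reviewer adjudicates, and state to which of them the finality rule applies.
2. Step one: the Reviewer rates severity, seriousness and, where feasible, event category from a narrative with group, device and procedure names redacted. These ratings are locked.
3. Step two: the intervention actually received is disclosed to the same Reviewer, who then judges only relationship and anticipated or unanticipated status.
4. Keep the investigator's ratings and tabulate them beside the Reviewer's, by arm.
5. Record for each event whether redaction was feasible. State as limitations that many device-specific narratives reveal the arm, and that bias in relatedness and in site-level capture remains.

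The cost is modest: redaction by data management and a two-part adjudication form. No second reviewer is needed, and visits and treatment do not change. Site reporting of unanticipated device effects to the sponsor within 24 hours under Section 9.6 need not wait for either step.
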